5. RATIONALE AND BACKGROUND

Anaemetron I.V. Infusion 500 mg (hereinafter referred to as "this drug") is an injection of metronidazole, which has been used for a long time in Japan. Metronidazole has a strong antibacterial or antiprotozoan activity against obligate anaerobes or protozoa respectively; for which, it is recommended in various domestic and overseas guidelines and textbooks, and highly regarded as a therapeutic method for anaerobic infection.

Anaerobic infection developed in patients with severe underlying diseases frequently becomes more refractory or serious due to the patients' susceptibility to infection. Patients in such a serious condition often have difficulties taking oral medications, and thus, metronidazole injection would be beneficial.

Such background warrants the great clinical significance to make metronidazole injection clinically available; for which, Pfizer obtained the approval to manufacture and market this drug in Japan in July 2014.

The drug use investigation of Anaemetron I.V. Infusion 500 mg (hereinafter referred to as "this study") shall be conducted to collect information regarding the occurrence by type of adverse reactions associated with this drug in daily clinical practice, and information regarding the quality, effectiveness, and safety of this drug. The information collected from this study shall be used to provide proper use information and prepare documents for the application of re-examination.

This study shall be conducted in strict compliance with the "MHLW Ordinance on the Standard for Post-Marketing Studies and Clinical Trials of Medical Products" (MHLW Ordinance No. 171 dated December 20, 2004).

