7.3.2. Targeted drug use record

The following will be recorded for the targeted drug.

- [1] Daily dose
- [2] Number of doses per day
- [3] Treatment period (start date/end date)
- [4] Reason for change of dose

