9.5. Single reference safety document

A Single Reference Safety Document (SRSD) refers to a document that contains the information on the known safety profile. The package insert of this drug will be the SRSD in this study. Pfizer Japan Inc. will evaluate the safety information reported by the investigator during the study period using the SRSD.

The investigator will also prescribe the drug and give the drug administration guidance based on the SRSD.

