5.4. Subgroups

Subgroup analyses of safety will be performed for the following patient background factors.

- Presence or absence of hepatic dysfunction
- Presence or absence of renal dysfunction
- Children (<15 years), adults (≥15 to <65 years), elderly (≥65 years)
- Diagnosis* (anaerobic infection, infectious enterocolitis [incl. pseudomembranous colitis], amebic dysentery)

* The same patient may have multiple diagnoses. In such case, additional subgroups may be added (e.g., anaerobic infection plus infectious enterocolitis).

Subgroup analyses of safety will also be performed according to the following factors:

- Pregnant and parturient women (pregnancy confirmed)
- Prior treatment (medication for infection) [absent, present]
- Concomitant medications (medication for infection) [absent, present]
- Maximum number of daily doses (1, 2, 3, 4, or >4 times)
- Dose escalation [absent, present]
- Overdose ** [absent, present]

** Patients who have had a daily dose of >500 mg or had >4 doses a day are defined as having experienced overdose.

Patients in whom Anaemetro might have been contraindicated per the package insert (hereinafter referred to as contraindicated patients) will be sampled from the registry according to separately-specified criteria and be analyzed for the safety of Anaemetro as a subgroup analysis.

Subgroup analyses of effectiveness will be performed for the following patient background factors.

- Presence or absence of hepatic dysfunction
- Presence or absence of renal dysfunction
- Children (<15 years), adults (≥15 to <65 years), elderly (≥65 years)
- Diagnosis* (anaerobic infection, infectious enterocolitis [incl. pseudomembranous colitis], amebic dysentery)

* The same patient may have multiple diagnoses. In such case, additional categories may be added (e.g., anaerobic infection plus infectious enterocolitis).

Subgroup analyses of effectiveness will also be performed according to the following factors:

- Prior treatment (medication for infection) [absent, present]
- Concomitant medications (medication for infection) [absent, present]
- Maximum number of daily doses (1, 2, 3, 4, or >4 times)

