- Maximum dose per single dose [< 500 mg, 500 mg, > 500 mg]
- Mean dose per single dose [< 500 mg, 500 mg, > 500 mg]
- Mean dose per single dose (continuous)
- Maximum number of daily doses [1, 2, 3, 4, > 4 times]
- Mean number of daily doses [< 1 time, 1 time, > 1 to < 2 times, 2 times, > 2 to < 3 times, 3 times, > 3 to < 4 times, 4 times, > 4 times]
- Mean number of daily doses (continuous)
- Dose escalation [absent, present]
- Overdose [absent, present].

The duration of treatment is from the initial day of administration in this Study to the last confirmed day of administration, and is the actual dosing days that excludes the period during which Anaemetro is suspended.

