8.2.3.4. Subgroup Analysis

The number and proportion of patients who experienced at least one adverse reaction will be tabulated for each factor specified in Section 5.4. To evaluate the relationship between patient background factors and the development of adverse reactions, the analysis based on risk ratio and risk difference specified in Section 8.1.3 will be performed. For subgroups with

risk ratio ≥ 2 or ≤ 0.5 , the number and proportion of patients who experienced adverse reaction will be summarized for each factors, using SOCs and PTs. It should be noted that if adverse reactions developed in less than a total of 10 patients, the risk ratio and risk difference will not be calculated, although the proportion will be presented for each factors.

The number and proportion of patients who experienced adverse reaction will be summarized by maximum number of daily doses, based on SOCs and PTs. Similarly, the number and proportion of patients who experienced serious adverse reaction will be summarized by maximum number of daily doses.

Listing of adverse reactions that developed in contraindicated patients will be tabulated. In addition, the number and proportion of those contraindicated patients who experienced adverse reactions will be tabulated by SOC and PT, as necessary.

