10.2. Appendix 2: Example of Categorizations for Risk Ratio Analysis

Exploratory categorization factors might be added to the set below. If an additional factor is one that categorized by absent or present, “absent” will be chosen as the reference.

| Categorization item | Categories | Reference |
|--|--|---------------------|
| Age | [<65 years, ≥65 years] | <65 years |
| Diagnostic name 1 | [anaerobic infection, infectious enterocolitis] | anaerobic infection |
| Diagnostic name 2 | [anaerobic infection, amebic dysentery] | anaerobic infection |
| Diagnostic name 3 | [anaerobic infection, anaerobic infection plus infectious enterocolitis] | anaerobic infection |
| Hepatic dysfunction | [absent, present] | absent |
| Renal dysfunction | [absent, present] | absent |
| Prior treatment (medication for infection) | [absent, present] | absent |
| Concomitant medications (medication for infection) | [absent, present] | absent |
| Number of daily Anaemetro doses (1) | [1 time, 3 times] | 3 times |
| Number of daily Anaemetro doses (2) | [2 times, 3 times] | 3 times |
| Number of daily Anaemetro doses (3) | [3 times, 4 times] | 3 times |
| Number of daily Anaemetro doses (4) | [3 times, >4 times] | 3 times |
| Dose escalation | [absent, present] | absent |

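### The SAP's overdose flag cuts the daily dose at 500 mg, so 500 mg given two, three or four times a day counts as overdose

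*SAP*

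**What the plan says.** SAP 5.4 lists overdose (absent or present) among the safety subgroup factors, with this footnote: "Patients who have had a daily dose of >500 mg or had >4 doses a day are defined as having experienced overdose". The two limbs are joined by *or*.

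The flag is used in two places. SAP 8.2.3.4 says: "The number and proportion of patients who experienced at least one adverse reaction will be tabulated for each factor specified in Section 5.4". SAP 8.2.2 also lists overdose as a row of the exposure table.

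Three other places bear on what the threshold should be:

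- SAP 8.2.2 applies the 500 mg figure to a different quantity: "Maximum dose per single dose [< 500 mg, 500 mg, > 500 mg".
- SAP Appendix 2 sets three times a day as the reference in all four dose-frequency contrasts, for example "Number of daily Anaemetro doses (2) | [2 times, 3 times] | 3 times".
- Protocol 9.5 names the reference for the known safety profile: "The package insert of this drug will be the SRSD in this study".

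Neither document defines overdose in any other way, and neither states the approved dose.

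**The concern.** Five hundred milligrams is the strength of one infusion (Protocol section 5). Used as a daily limit, it makes a second infusion on the same day an overdose. The SAP elsewhere treats two, three and four doses a day as ordinary exposure categories, and three as the reference. The second limb also implies that up to four doses a day is acceptable on frequency, which the first limb contradicts for any patient on 500 mg doses.

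If the rule is programmed as written, the exposure table in 8.2.2 reports multiple daily dosing as overdose. The table in 8.2.3.4 then compares patients on 500 mg a day or less with everyone else, under an overdose label. Patients who really received too much are mixed with those who did not. The final analysis supports the re-examination application (SAP section 3), so the label would reach a regulator.

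A literal reading is likely to be carried through, because daily dose is a recorded field (Protocol 7.3.2) that matches the SAP's wording, whereas single dose has to be derived.

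**Working it through.** The plan gives no figure of its own for the size of the overdose group, so the check is to apply the rule.

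**Inputs.** Strength 500 mg (Protocol section 5); rule from SAP 5.4; single-dose categories and frequencies of 1, 2, 3, 4 and more than 4 a day from SAP 8.2.2.

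**Step 1: apply the rule.** Daily dose = single dose × doses per day.

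| Regimen | Daily dose | As written: daily > 500 mg or > 4 doses | Single dose > 500 mg or > 4 doses | Daily > 2000 mg or > 4 doses |
|---|---|---|---|---|
| 500 mg × 1 | 500 mg | no | no | no |
| 250 mg × 2 | 500 mg | no | no | no |
| 250 mg × 3 | 750 mg | **yes** | no | no |
| 500 mg × 2 | 1000 mg | **yes** | no | no |
| 500 mg × 3 | 1500 mg | **yes** | no | no |
| 500 mg × 4 | 2000 mg | **yes** | no | no |
| 500 mg × 5 | 2500 mg | yes | yes | yes |
| 750 mg × 1 | 750 mg | yes | yes | no |
| 750 mg × 2 | 1500 mg | yes | yes | no |

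The four bold entries are flagged as written and by neither alternative.

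**Step 2: does the result depend on exactly 500 mg per dose?** The daily limb fires once the single dose exceeds 500/n for n doses a day: 250 mg at n = 2, about 167 mg at n = 3, 125 mg at n = 4. At three doses a day any single dose above about 167 mg is flagged, so it does not.

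**Step 3: what does the second limb add?** Only patients on five or more doses whose daily total is at most 500 mg, that is 500/5 = 100 mg or less per dose. For a 500 mg product that is almost nobody, which suggests that the first limb was not meant as a daily limit.

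**Step 4: illustrate the dilution.** Suppose T patients are truly over (single dose above 500 mg, or more than four doses a day). The written rule catches all of them, inside a flagged group of size F. If everyone else has equal risk, then

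observed RR = 1 + (T/F) × (true RR − 1),

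and the true RR needed for an observed RR of 2 is 1 + F/T. SAP 8.2.3.4 uses a risk ratio of at least 2, or at most 0.5, to trigger tables by SOC and PT. T and F are assumptions, out of 100 patients.

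| T | F | Observed RR when true RR = 2 | True RR needed to observe 2 |
|---|---|---|---|
| 5 | 25 | 1 + 5/25 = 1.20 | 6 |
| 5 | 50 | 1 + 5/50 = 1.10 | 11 |
| 5 | 90 | 1 + 5/90 = 1.06 | 19 |
| 10 | 25 | 1.40 | 3.5 |
| 10 | 50 | 1.20 | 6 |
| 10 | 90 | 1.11 | 10 |

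**The case against.** The arithmetic in Step 1 is not open to dispute. The case on the other side is that little depends on it.

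*The risk ratio may not be planned for this factor.* SAP 8.2.3.4 ties the risk ratio to patient background factors; section 5.4 puts overdose in a second list, and Appendix 2 has no overdose row although it has one for dose escalation. This is a fair doubt but not a decisive one. Appendix 2 is headed as an example and covers other factors from the second list. The counts and proportions are in any case required for every factor in 5.4.

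*A correct flag would tell us little either.* This stands. Take 5 overdosed and 95 other patients, a 10% baseline risk, and at least 10 patients with reactions, below which the SAP calculates no risk ratio. Exact binomial enumeration gives a 71% chance that the two-sided trigger fires when the true risk ratio is 1, and 68% when it is 2. At 20% baseline the figures are 50% and 59%. At 10% baseline, the chance of reaching 10 patients with reactions is only 55% to 61%. Step 4 therefore shows the direction and scale of the dilution, not a usable signal that would otherwise have been found. It also assumes no dose-response among patients not truly over-dosed.

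*Overdose is covered elsewhere.* Partly. Overdoses are reported within 24 hours and recorded on the CRF (Protocol 9.1). Section 8.2.3.4 tabulates reactions by maximum number of daily doses, which covers the second limb, and section 9 of the SAP plans patient listings. No other planned table sets single doses above 500 mg against adverse reactions.

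*It is probably a one-word slip, and the right limit is not in the documents.* Both points are reasonable. The first makes the repair easy, and the second is why it needs checking against the package insert.

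**Conclusion.** The concern holds. As written, the definition classifies 500 mg given two, three or four times a day as overdose, conflicts with the single-dose cut in SAP 8.2.2 and the reference frequency in Appendix 2, and leaves its own second limb almost without effect. It is an operative derivation rule: followed literally, it produces a mislabelled exposure row and a mislabelled adverse reaction table.

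The conclusion needs only the quoted rule and multiplication. That 500 mg is the usual single dose is inferred from the product strength and the 8.2.2 categories, and Step 2 shows that the result does not hang on it. That *daily* stands for *single* is also an inference. The dilution figures rest on assumed counts and should be read only as illustration.

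The consequence is limited. The SAP declares its tests exploratory (4.1), and overall adverse reaction incidence, clinical response rate, eradication rate and sample size do not depend on the flag. It should be corrected before the final tables are run, but it does not threaten the study's main results.

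**What to change.** In SAP 5.4, change the first limb to more than 500 mg per single dose, matching the categories in 8.2.2, and keep the limb for more than four doses a day. A daily limit of more than 2000 mg (4 × 500 mg) is an alternative. The SAP should state which is used, because they differ: 750 mg twice a day (1500 mg) is flagged by the single-dose limb and not by the 2000 mg limit. Confirm the chosen threshold against the package insert named in Protocol 9.5.

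Derive single dose as recorded daily dose divided by "Number of doses per day" (Protocol 7.3.2), taken over each dosing record. This is an average within the day and can miss one large dose among unequal ones, which the SAP should acknowledge. Re-derive the flag for 8.2.2 and 8.2.3.4, and include a programming check that 500 mg three times a day is not flagged.

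The cost is one SAP definition and one derived variable, with no new data.

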6. ENDPOINTS AND COVARIATES

6.1. Safety Endpoints

Safety endpoints include:

- Adverse reactions: Adverse events determined to be related to Anaemetro by the physician
- Adverse events: All-causality adverse events
- Serious adverse reactions or events: Adverse reactions or adverse events in which the seriousness was determined to be serious by the physician
- Safety specification items: The following events will be handled as safety specification items:
 - Central nervous system (CNS) disorder: Events that were considered as a central nervous system disorder by the physician and had a check mark on “yes/unknown” in the corresponding AE item of the CRF
 - Peripheral nerve disorders
 - Aseptic meningitis
 - Toxic epidermal necrolysis, oculomucocutaneous syndrome
 - Acute pancreatitis
 - Leukopenia, neutropenia
 - Carcinogenicity

All safety specification items except central nervous system disorder and all events included in safety specifications will be defined according to MedDRA SMQ, System Organ Classes (SOCs), or Preferred Terms (PTs), or classified according to a classification table prepared using observed AEs based on the risk management plan (RMP). Safety specification items are in accordance with the RMP of Anaemetro submitted in January 2017.

6.2. Effectiveness Endpoints

6.2.1. Clinical Response

At the end of observation period or at the time of discontinuation, clinical response will be assessed by the physician from a comprehensive perspective according to the criteria below. If this drug is administered continuously for more than 8 weeks, the clinical response should be evaluated comprehensively at Week 8. The definitions are as follows.

- Reason for the use: anaerobic infection:
 - Effective: Clinical symptoms accompanying the infection observed at the initiation of treatment with this drug has improved at the time of assessment, and treatment

with other antibacterial drugs after the time of assessment is determined not necessary.

- Not effective: "Effective" criteria are not met.
- Indeterminate: Clinical response is difficult to evaluate.

- Reason for the use: infectious enterocolitis (incl. pseudomembranous colitis):
 - Effective: Clinical symptoms accompanying the infection observed at the initiation of treatment with this drug has improved at the time of assessment, and treatment with other antibacterial drugs after the time of assessment is determined not necessary.
 - Not effective: "Effective" criteria are not met.
 - Indeterminate: Clinical response is difficult to evaluate.
- Reason for the use: amebic dysentery:
 - Effective: Clinical symptoms accompanying the infection observed at the initiation of treatment with this drug has improved at the time of assessment, and treatment with other antibacterial drugs other than antiamebic agents (paromomycin, etc.) after the time of assessment is determined not necessary.
 - Not effective: "Effective" criteria are not met.
 - Indeterminate: Clinical response is difficult to evaluate.

In this Study, clinical response may be evaluated for each diagnosis. If the same patient have multiple diagnoses under investigation with different clinical response, the patient will be handled as a “inconsistent clinical response” case for overall clinical response evaluation is difficult.

6.2.2. Microbiological Response

At the end of observation period or at the time of discontinuation, microbiological response will be assessed by the physician according to the criteria below. If this drug is administered continuously for more than 8 weeks, the clinical response should be evaluated comprehensively at Week 8.

- Eradication: Pathogen is not detected in the specimen appropriately collected following administration of this drug.
- Presumed eradication: Pathogen is presumed eradicated if the treatment improves or resolves the clinical symptoms, and a specimen suitable for the test is no longer available in the original infection focus.
- Partial eradication: Pathogen is partially detected in the specimen appropriately collected following administration of this drug.
- Persistence: No improvement of clinical symptoms is confirmed, and the pathogen is detected in the infection focus.

- Indeterminate: A microbiological test was conducted, but no pathogen could be isolated or estimated. Or a microbiological test was not conducted due to various reasons.

6.2.3. Eradication/Persistence of Each Pathogenic Organism/Strain

Eradication/persistence of each pathogenic organism/strain may be determined based on the pathogenic organism/strain detected before Anametro treatment in microbiological testing. The survival of pathogenic organism/strain is defined as follows.

- Eradication: The pathogenic organism/strain detected at the commencement of treatment was not detected after treatment (the bacterial load is “-”) or no specimens could be collected. When the pathogenic organism is *Entamoeba histolytica*, it is considered eradicated if amebic protozoa test had been positive before treatment and changed to negative after treatment.
- Persistence: The pathogenic organism/strain detected at the commencement of treatment was detected from a specimen after treatment. When the pathogenic organism is *Entamoeba histolytica*, it is considered persistent if amebic protozoa test had been positive before treatment and remained positive after treatment.
- Indeterminate: Microbiological test after treatment was not performed at all for various reasons.

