7.3.4.2. Other tests

Microbiological test

Record the pathogen for which this drug is used, and the expected results of test on the causative organism. Record the following information before the initiation of treatment with this drug, during the observation period, and at the completion of observation period.

- [1] Specimen
- [2] Pathogen, and the name of causative bacterial strain
- [3] Date of sampling
- [4] Test method
- [5] Pathogen result (Semi-quantitative) (-, +, ++, +++, Unknown)
- [6] MIC of this drug
- [7] Presence/absence of ameba protozoa

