7.3.6. Effectiveness evaluation

(1) Clinical response

The clinical response of this drug should be evaluated comprehensively at the completion of the observation period, and the results should be recorded.

If this drug is administered continuously for more than 8 weeks, the clinical response should be evaluated comprehensively at Week 8.

- Effective
- Not effective
- Indeterminate (the reason should be recorded.)

The assessment criteria shall be as follows:

Table 2. Assessment criteria for [anaerobic infection] / [infectious enterocolitis (including pseudomembranous colitis)]

Assessment	Definition
Effective	Clinical symptoms accompanying the infection observed at the initiation of treatment with this drug has improved at the time of assessment, and treatment with other antibacterial drugs after the time of assessment is determined not necessary.
Not effective	"Effective" criteria are not met.
Indeterminate	Clinical response is difficult to evaluate.

Table 3. Assessment criteria for [amebic dysentery]

Assessment	Definition
Effective	Clinical symptoms accompanying the infection observed at the initiation of treatment with this drug has improved at the time of assessment, and treatment with other antibacterial drugs other than antiamebic agents (paromomycin, etc.) after the time of assessment is determined not necessary.
Not effective	"Effective" criteria are not met.
Indeterminate	Clinical response is difficult to evaluate.

Any clinically problematic finding compared to the initiation of treatment should be recorded in details in the AE column.

(2) Rationale for clinical response assessment

The rationale for the clinical response assessment ("Effective" or "Not effective"), on the disease for which this drug is used, should be recorded.

[Anaerobic infection]

General clinical findings, body temperature, WBC count, CRP level, imaging, and others

[Infectious enterocolitis (including pseudomembranous colitis)]

General clinical findings, Clostridium difficile TOXIN test, frequency of diarrhea, body temperature, abdominal pain, and others

[Amebic dysentery]

General clinical findings, ameba test, frequency of diarrhea, body temperature, abdominal pain, and others

(3) Microbiological response assessment

Microbiological response at the completion of observation period compared to prior to the initiation of treatment with this drug should be assessed, and the results should be recorded.

Table 4. Assessment criteria for microbiological response

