| | | | 
serious adverse reactions and serious adverse events was deleted.
 
 - An analysis plan for potentially contraindicated patients was added. - The description for the analysis of the incidence of adverse reactions by the experience of 4-times-a-day dosing for each SOC and PT was moved to this subsection of subgroup analyses as an analysis by maximum number of daily doses. - A subgroup analysis for the incidence of serious adverse reactions by maximum number of daily doses was added to the set of subgroup analyses. 
8.2.3.5. Exploratory Analysis
 
 - Due to the limited number of patients with AEs, the plan for logistic regression was deleted. 
8.2.4.1. Clinical Response
 
 - A plan of analyzing the response rate for each pathogenic organism/strain by diagnosis was added. - The plan of summarizing data by presence of 4-times-a-day dosing was changed to by maximum number of daily doses. 
8.2.4.2. Microbiological Response
 
 - The plan of summarizing data by presence of 4-times-a-day dosing was changed to by maximum number of daily doses. 
8.2.4.3. Eradication/Persistence of Each Pathogenic Organism/Strain
 
 - Considering the fact that the same organism was detected from the same patient multiple times from different test materials as a pathogenic organism, it was determined that all the collected bacterial information should be used and the analysis of pathogenic organism/strain was changed from in terms of the number of patients to in terms of the number of microbes. - The summarization by presence of 4-times-a-day dosing was changed to by maximum number of daily doses. - The analysis plan by diagnosis name and by presence of central nervous system disorder was deleted. 
8.2.4.4. Subgroup Analysis
 
 - Clarified that each subgroup analysis will be performed in terms of risk ratio and risk difference. 
8.2.4.5. Exploratory Analysis
 |

| Version | Date | Author(s) | Summary of Changes/Comments |
|---------|-------------|-----------|--|

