8.2.4.3. Eradication/Persistence of Each Pathogenic Organism/Strain

In the microbiological response analysis set, the number and proportion of microbes that were considered eradicated will be calculated by pathogenic organism/strain detected by the pretreatment microorganism test. The 95% CI of eradication rate will also be calculated, using indeterminate cases subtracted from the denominator. Similar calculations will be tabulated by diagnosis and by maximum number of daily doses. The eradication rate for a specific pathogenic organism/strain can be calculated by the following formula:

Eradication rate for a specific pathogenic organism/strain (%) = (number of pathogenic organism/strain/number of pathogenic organism/strain detected pretreatment except “indeterminate”) × 100.

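### SAP 6.2.3 scores an unsampled bacterial organism as eradicated without the symptom condition of 6.2.2, and 8.2.4.3 puts a CI for independent units on isolates that can repeat within a patient

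*SAP*

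**What the plan says.** **No-specimen rule.** SAP 6.2.3 defines organism-level eradication as non-detection after treatment "or no specimens could be collected". For *Entamoeba histolytica* it uses a separate rule, a change from a positive to a negative test. An organism is indeterminate if "Microbiological test after treatment was not performed at all for various reasons".

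**Patient-level rule.** SAP 6.2.2 and protocol Table 4 use the same wording: "Pathogen is presumed eradicated if the treatment improves or resolves the clinical symptoms, and a specimen suitable for the test is no longer available". Under protocol 7.3.6 (3) this response, "compared to prior to the initiation of treatment with this drug should be assessed, and the results should be recorded", so the rating is a collected item.

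**Result codes.** Protocol 7.3.4.2 lists "Pathogen result (Semi-quantitative) (-, +, ++, +++, Unknown".

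**Analysis.** In SAP 8.2.4.3, "the number and proportion of microbes that were considered eradicated will be calculated by pathogenic organism/strain detected by the pretreatment microorganism test". Then: "The 95% CI of eradication rate will also be calculated, using indeterminate cases subtracted from the denominator". Section 8.1.3 sets the exact method for intervals on proportions. The SAP change log gives the reason for counting microbes: "Considering the fact that the same organism was detected from the same patient multiple times from different test materials as a pathogenic organism". All bacterial records are to be used.

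**Companion table.** The last paragraph of SAP 8.2.4.2 plans a second rate per organism, by diagnosis. It counts patients rated eradication or presumed eradication.

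**The concern.** A missing specimen is evidence of eradication only if there was nothing left to sample because the patient got better. Section 6.2.2 makes that explicit and 6.2.3 does not. Take an unimproved patient from whom no specimen could be obtained. Under 6.2.2 the patient cannot be rated presumed eradication, yet under 6.2.3 the organism can enter the 8.2.4.3 numerator. One report would then carry two eradication rates for the same organism and diagnosis, on different rules and without explanation.

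The second issue is independent of the first. Repeats of one organism in one patient tend to share an outcome. An exact binomial interval treats each as new information and can be too narrow for its label.

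**Working it through.** **Plan's own figure.** The plan gives no figure for organism-level eradication. Its one design figure, 95% probability of seeing a 3% adverse reaction in 100 patients, reproduces (1 − 0.97^100 = 95.2%) and is not involved here.

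**Step 1. Definitions side by side** (organisms other than *E. histolytica*)

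| Situation after treatment | 6.2.2, patient | 6.2.3, organism |
|---|---|---|
| Tested, not detected | Eradication | Eradication |
| No specimen available, symptoms improved | Presumed eradication | Eradication |
| No specimen available, symptoms not improved | Not presumed eradication | Eradication |
| Test not performed | Indeterminate | Indeterminate |
| Result code Unknown | Left to the physician's rating | No category fits |

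The third row is the inconsistency. It follows from the text alone.

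**Step 2. Effect on the rate** (all counts assumed)

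Let E be tested negative, P detected, S unsampled, and u the unsampled organisms from unimproved patients. The current rate is (E + S)/(E + P + S). With the symptom condition, and the rest indeterminate, it is (E + S − u)/(E + P + S − u). With E = 16, P = 8, S = 6:

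| u | Rate | Exact 95% CI |
|---|---|---|
| 0 (equals the current text) | 22/30 = 73.3% | 54.1-87.7 |
| 2 | 20/28 = 71.4% | 51.3-86.8 |
| 4 | 18/26 = 69.2% | 48.2-85.7 |
| 6 | 16/24 = 66.7% | 44.7-84.4 |

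The fall is 0 to 6.7 points. In the extreme where every unsampled organism is from an unimproved patient, and two thirds of tested isolates are negative, the fall depends on the unsampled share of 30 isolates:

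- 10% (3): 21/30 = 70.0% to 18/27 = 66.7%, a fall of 3.3 points.
- 20% (6): 73.3% to 66.7%, a fall of 6.7 points.
- 40% (12): 24/30 = 80.0% to 12/18 = 66.7%, a fall of 13.3 points.

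**Step 3. Effect of repeats on the interval** (assumed)

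A simple case: 20 patients, two isolates each, always concordant, 16 patients cleared. Counted as isolates, 32/40 gives 64.4-90.9. Counted as patients, 16/20 gives 56.3-94.3. The estimate is 80% in both.

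For coverage, each patient's total was taken as beta-binomial with within-patient correlation (ICC) 0.2, 0.3, 0.5, 0.8 or 1.0. The distribution over 10, 20 or 30 patients was enumerated exactly. Coverage of the nominal 95% Clopper-Pearson interval on all isolates was averaged over true rates of 60% to 95% in steps of 1 point.

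| Repeats | ICC 0.2-0.3 | ICC 0.5-1.0 |
|---|---|---|
| None | 97.3-98.4% | 97.3-98.4% |
| Two isolates in 30% of patients | 95.8-97.5% | 92.8-96.7% |
| Two in half | 95.2-97.2% | 90.6-95.8% |
| Two in all | 93.7-96.1% | 86.6-93.5% |
| Three in all | 90.3-94.0% | 76.4-88.4% |

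The exact method is conservative when there are no repeats, and this absorbs a small number of them. Coverage falls clearly below 95% only when repeats are common and correlated.

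**The case against.** **A patient-based table already exists.** The per-organism rate in 8.2.4.2 uses patients and the 6.2.2 rating, so it carries the symptom condition. This stands and lowers the priority. It does not replace 8.2.4.3: it applies one whole-patient rating to every organism, and it is not planned by organism and number of daily doses together. Nothing tells the reader why the two rates differ.

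**6.2.3 is its own scheme.** It is worded as optional, has no partial category, and drops symptoms from persistence as well. Two endpoints need not agree. That is fair, but a detected organism is persistent whatever the symptoms, whereas an uncollected specimen says nothing without them. The SAP does not say that failure to collect implies recovery.

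**The data may separate the cases.** Could not be collected and not performed can be told apart in words. Protocol 7.3.4.2 lists no item for this, but the case report form is not in the documents, so a missing field cannot be asserted. Only the Unknown code is visibly unmapped.

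**Counting microbes was deliberate.** It was chosen so that all bacterial information is used, and the documents do not say how often repeats occur. At low correlation the loss is slight or nil. This stands.

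**Stronger readings.** A reader might infer that the plan inflates the drug's effectiveness. The documents do not support that. The true state of an unsampled organism is unknown, so this is an inconsistent convention and not a demonstrated bias. A reader might also extend the point to *E. histolytica*, but its rule requires a negative test.

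**Conclusion.** The point holds at low priority. As written, 6.2.3 lets an unsampled organism from an unimproved patient count as eradicated in 8.2.4.3, which 6.2.2 and protocol Table 4 would not accept as presumed eradication. Separately, the interval in 8.2.4.3 (exact by way of 8.1.3) assumes an independence that repeated isolates do not have.

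The size cannot be known from the documents. On the assumed 30 isolates with 6 unsampled, the rate moves by 0 to 6.7 points, within the interval. Over ICC 0.2 to 1.0, mean coverage is about 93-98% with two isolates in 30% of patients, 87-96% with two in all and 76-94% with three in all. The loss is therefore material only if repeats are both common and correlated. The study is not confirmatory (SAP 4.1), and neither the primary clinical response rate nor any rate in 8.2.4.2 is touched.

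**What to change.** 1. **SAP 6.2.3.** Outside the *E. histolytica* test rule, count a no-specimen organism as (presumed) eradicated only if improvement is recorded: either the physician's rating is presumed eradication, or the clinical response for that diagnosis is effective. Otherwise count it as indeterminate. Put a post-treatment result of Unknown in indeterminate too. The clinical-response route matters in mixed infections: a patient rated eradication on one cultured organism may have a second organism with no specimen, and the rating alone would wrongly drop it.
2. **SAP 8.2.4.3.** Base the rate and interval on one record per patient per organism: persistent if any post-treatment specimen is positive, eradicated if at least one is negative and none positive, and rule 1 if there is no specimen. A patient-clustered interval is the alternative. Keep isolate-level counts as a descriptive supplement, so that all bacterial information is still shown.
3. **Both tables.** State how 8.2.4.3 relates to the per-organism table in 8.2.4.2.

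**Cost.** SAP wording and a derivation rule. No new data are needed, because the protocol already collects the microbiological rating and the clinical response. The rate may be slightly lower, with a smaller denominator and a wider interval. An effective response also requires that no further antibacterial treatment is needed, so some improved patients' unsampled organisms will still become indeterminate.
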